	technologies for glaucoma home monitoring would be feasible and	
	acceptable.	
	Data collection RO1 - Patients	
	Once consented, visual field and intra-ocular pressure data will be obtained from patients using a standard visual field test and IOP measurement in clinic at baseline and another at study completion (4 months). Data will be recorded (manually and then entered electronically) on a Baseline Case Report Form (CRF). Demographic data (e.g. age, gender, education, disease status, previous eye treatments) will also be collected from the medical notes and recorded on the case report form by the Research Nurse In addition to using the home monitoring equipment, patients will be invited to participate in interviews (using semi-structured topic guides to direct the conversation) to explore acceptability of home monitoring generally and focus on the requirements (both in the short, medium, and long term) of the digital	
	technologies under investigation. Interviews will be conducted by the I-TRAC	
	Research Fellow once patients have completed the 4-month home monitoring measurements.	
	Patients will be sent (either by email or post) a weekly prompt to conduct their eye measurements. They will also be sent a prompt of their 4 month clinic visit a few days before attendance. Clinical sites will also be sent a prompt the day before a patient visit is due.	
	Data collection RO1 - Ophthalmologists Two focus groups with 6–8 ophthalmologists per group (samples deemed appropriate in this context) will be conducted by the I-TRAC Research Fellow and a facilitator. Again data collection will be guided by semi-structured topic guides to facilitate discussion.	
	Data collection RO1 – Researchers and NHS Staff Up to 6 members of relevant research teams will be invited to interview (with data collection guided by semi-structured topic guides) to share their experience of delivering studies in this setting with a particular focus on the barriers and facilitators to design and delivery. These interviews will be conducted by the I-TRAC Research Fellow.	

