RO1 will collect qualitative data from interviews and focus groups and will also collect quantitative data through the weekly measurement using the home monitoring equipment. Two types of clinical outcome data will be collected: 1. Tonometry data; and 2. Perimetry data. The home tonometer measures intraocular pressure (IOP) and presents data on a scale of 0-70 (0 = low pressure, 70 = high pressure), with most patients measuring between 10-30. Visual field tests using the home perimeter present a mean deviation, which quantifies the severity of the visual field loss, presented on a scale of 0-30 (0 = no damage, 30 = very damaged). These clinical outcome data collected using the home perimetry (visual field, 0-30) and tonometry (IOP, 0-70) technology will be analysed using descriptive statistics to describe the patient sample and the changes (if any) in the measurements over time. We will also confirm that we are able to get repeated measures through home monitoring. The data collected using the home monitoring technology will be compared to the clinic visit measurements at 4 months to qualitatively assess the agreement between home and hospital-based monitoring. We will use Bland-Altman methodology to assess the limits of agreement between the two IOP measurements. An added feature of the data we are collecting is repeated measures of home IOP. There are several ways then to use the data. We will outline the full detail in a statistics analysis plan before the study commences, but in brief agreement comparisons of interest will be agreement between 4-month clinic IOP and:

- Mean IOP over period (using random effect models outline in Myles and Cui [37]
- Most recent home IOP measurement
- Highest IOP measurement.
- The other quantitative data collected in RO2 relates to recruitment rates, adherence to intervention (assessed by number of weekly measurements completed), and requirements for further training (assessed by additional training received: face-to-face or over telephone). These data will be analysed using descriptive statistics and presented as frequencies.

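### Section 4.2 quantifies home-versus-clinic agreement for IOP only and names no quantified agreement for visual field, although both home and clinic visual fields are collected (minor)

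*Protocol*

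**What the plan says.** All places are in the WP2-4 protocol. Section 18.1 puts two technologies under assessment, a home perimeter and a home tonometer, and patients use both weekly for 4 months.

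Both give numbers. Section 4.2 (RO1, Patients) states: "The home tonometer measures intraocular pressure (IOP) and presents data on a scale of 0-70". For the perimeter it states: "Visual field tests using the home perimeter present a mean deviation, which quantifies the severity of the visual field loss, presented on a scale of" (the range given is 0 to 30). Section 3.1 supplies the hospital side of the comparison: "visual field and intra-ocular pressure data will be obtained from patients using a standard visual field test and IOP measurement in clinic", once at baseline and once at 4 months.

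On analysis, section 4.2 says three things:

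- Data from both devices "will be analysed using descriptive statistics to describe the patient sample and the changes (if any) in the measurements over time".
- The home data, with no distinction between devices, are to be "compared to the clinic visit measurements at 4 months to qualitatively assess the agreement between home and hospital-based monitoring".
- For tonometry alone, a quantitative method is named: "We will use Bland-Altman methodology to assess the limits of agreement between the two IOP measurements".

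It then remarks that home IOP is measured repeatedly and says that full detail will be given "in a statistics analysis plan before the study commences, but in brief agreement comparisons of interest will be agreement between 4-month clinic IOP and" three summaries of home IOP: the mean over the period, the most recent reading and the highest reading. No such comparison is listed for visual field.

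**The concern.** The protocol goes beyond silence on agreement. It describes the comparison as qualitative, then gives a quantitative method and a list of comparisons to one of its two devices. A statistician working from this text would produce limits of agreement for IOP and would find no instruction to do so for mean deviation.

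The protocol's own purposes make this worth correcting:

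- Section 4.1 justifies 45 patients by a size range recommended for estimating SDs that later sample-size calculations can use. Section 17.1 includes informing the design of a future evaluative study. The SD of home-minus-clinic mean deviation is a candidate input, and no named analysis produces it.
- Under RO2, section 18.1 takes both home IOP and home visual field results into a discussion of what result would trigger contact with the NHS. An unmeasured offset in home mean deviation would carry into that discussion.
- For the tonometer, section 18.1 already cites mean differences from the reference method (-1.31 to 0.7 mmHg, with one study at -2.7) and percentages within 3 or 5 mmHg. For the perimeter it cites only comparability and strong correlation. The device with less quantified agreement in the document is the one left without limits.

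**Working it through.** **The plan's own figure.** Three sites with 15 patients each give 3 × 15 = 45 (sections 4.1 and 19.1), inside the quoted range of 24 to 50. It reproduces, and this point does not dispute it. The protocol states no alpha, power, SD or margin for agreement.

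**Measure by measure.**

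| | IOP | Visual field |
|---|---|---|
| Home data | numeric, 0-70, weekly | mean deviation, 0-30, weekly |
| Clinic data | baseline and 4 months | baseline and 4 months; output scale not stated |
| General agreement statement | qualitative | qualitative |
| Bland-Altman limits named | yes | no |
| Specific comparisons listed | three | none |

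The columns differ in the last two rows and in whether the clinic scale is known.

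**Could sample size justify the difference?** Assume one home-clinic pair per patient, n pairs, and differences with standard deviation SD. The standard error of a 95% limit of agreement is

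SE = SD × √(1/n + 1.96²/(2(n − 1))).

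For n = 45:

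- 1/45 = 0.0222 and 3.8416/88 = 0.0437. They sum to 0.0659, so SE = 0.257 SD.
- 95% half-width of each limit: 1.96 × 0.257 = 0.503 SD with the normal multiplier, or 0.517 SD with t on 44 degrees of freedom.
- 95% half-width of the bias: t/√45 = 0.30 SD.
- 95% interval for the SD itself (chi-square, 44 df): 0.83 to 1.26 times the estimate.

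The protocol gives no drop-out or perimeter completion figure, so the smaller numbers of pairs below are assumptions to show the range:

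| Usable pairs | Half-width of each limit (t) | Half-width of bias | SD interval (× estimate) |
|---|---|---|---|
| 45 | 0.52 SD | 0.30 SD | 0.83 to 1.26 |
| 40 | 0.55 SD | 0.32 SD | 0.82 to 1.28 |
| 36 | 0.58 SD | 0.34 SD | 0.81 to 1.30 |
| 30 | 0.65 SD | 0.37 SD | 0.80 to 1.34 |
| 24 | 0.73 SD | 0.42 SD | 0.78 to 1.40 |

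For a given number of pairs, these values apply in SD units to any comparison of one reading per patient, so they hold equally for most recent home IOP against clinic IOP. Sample size is no reason to give limits to one device only. The SD of visual field differences is not in the document, so nothing can be stated in mean deviation units.

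**Which pairs are valid?** Appendices 4 and 6 allow the baseline and 4-month readings to come from the home equipment when a patient cannot attend. For such a patient the pair is home against home. It carries no information on agreement with the clinic and would tend to make agreement look better than it is. This applies to IOP as much as to visual field.

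**The case against.** The strongest reply has four parts.

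*The detail is deferred.* Section 4.2 calls its list brief and sends full detail to a statistical analysis plan. That stands in part: the plan is not shown and may quantify visual field agreement. A reader might infer that the study will yield no quantified agreement for perimetry, and the protocol alone cannot support that. But the deferral follows directly from the remark about repeated home IOP, and every comparison named is IOP, so it does not clearly bring visual field in.

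*The qualitative wording is not about visual field.* Correct. A reader might infer that the protocol singles out perimetry for judgement by eye. The sentence covers home data from both devices, and IOP then receives limits under that same sentence. The accurate statement is narrower: one general qualitative comparison for both devices, with a quantitative method added for one.

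*Agreement is not what the study is for.* Section 17.2 sets no primary outcome, and section 2 says that the study concerns feasibility and acceptability rather than measurement accuracy. This stands as a limit on importance. However, section 2 makes that remark to explain why home readings are not reviewed in real time. It does not explain why one device gets limits and the other does not. Nor does the protocol commit the future study to a perimetry endpoint, so the SD of differences is a plausible input and not a proven need.

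*The clinic scale is unknown.* This also stands. Section 3.1 mentions only a standard visual field test, without its output, scale or sign. Limits are meaningful only once both readings are on a common footing, so the fix must include that step.

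**Conclusion.** The point holds as a minor improvement. The protocol specifies a quantified home-versus-clinic agreement for IOP and none for visual field, while collecting visual fields in both settings, and its own figures give no reason for the difference. The qualitative wording also sits badly beside the Bland-Altman sentence that follows it and deserves correction for both devices.

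The size is what the added analysis would deliver: at 45 pairs, the bias to about ±0.30 SD and each limit to about ±0.50 to 0.52 SD of the differences, widening to ±0.73 SD at 24 pairs. This assumes one pair per patient, approximately normal differences, and a clinic mean deviation that can be put on the same scale and sign as the home value. The sample size, the objectives and the feasibility conclusions are not called into question.

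**What to change.** In section 4.2:

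1. Replace the wording on qualitative assessment with a quantitative assessment of agreement for both devices.
2. Add that the 4-month clinic visual field mean deviation will be compared with the most recent home mean deviation by Bland-Altman analysis. Report the bias, the SD of differences and the limits, each with a 95% confidence interval, and a plot of difference against mean so that any change in spread with severity can be seen.
3. State the clinic test's output, and express both readings on one scale and sign before differencing.
4. For visual field and IOP alike, exclude from the home-versus-clinic pairs any patient whose clinic reading was taken with the home equipment under Appendix 4 or 6, and report how many were excluded.

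A baseline comparison may be added under the same exclusion, but is optional. If the statistical analysis plan already contains this analysis, aligning section 4.2 with it is enough. If visual field agreement is deliberately left unquantified, one sentence should say why.

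The cost is a few lines of text and analysis on data already planned for collection, with no further measurements or patients. It does require recording which device produced each baseline and 4-month reading.

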1.1 Study Aims

The aim of this study is to determine the feasibility and acceptability of digital technologies to monitor glaucoma at home and inform the possible need and design of a definitive evaluative study.

1.2 Scope

The purpose of this document is to describe the membership, terms of reference, roles, responsibilities, authority, decision-making and relationships of the Study Steering Committee (SSC) for I-TRAC, including the timing of meetings, methods of providing information to and from the SSC, frequency and format of meetings and relationships with other trial committees.

1.3 Facilitation

The I-TRAC Research Fellow will be nominated as a Facilitator for the trial. The Facilitator will be responsible for the organisation of meetings and should be copied into all communications with and between the SSC.

2. Roles and responsibilities

2.1 Aims of SSC

To act as the oversight body for the I-TRAC study on behalf of the Sponsor and Funder.

2.2 Terms of reference

The role of the SSC is to provide oversight for the trial. It should also provide advice through its independent Chairman to the Project Management Group (PMG), and the funder, as appropriate, on all aspects of the study.

2.3 Specific roles of SSC

The rights, safety and well-being of the trial participants are the most important considerations and should prevail over the interests of science and society. The SSC's role will include, but not be restricted to, the following:

- provide expert oversight of the study
- maintain confidentiality of all study information that is not already in the public domain
- make decisions as to the future continuation (or otherwise) of the study
- monitor recruitment rates and encourage the PMG to develop strategies to deal with any recruitment problems including sites who fail to recruit adequately
- approve the protocol(s) and ensure appropriate ethical, & other approvals, are obtained
- review regular reports (e.g. follow-up rates) of the study (sent on behalf of the Project Management Group (PMG))
- assess the impact and relevance of any accumulating external evidence
- review protocol adherence and advise on sites that are deviating from the protocol
- approve any proposals by the PMG concerning any change to the design of the study, including additional substudies
- oversee the timely reporting of study results
- comment on the publication policy
- comment on the main study manuscript
- approve external requests for release of data or subsets of data including clinical data
- monitor compliance with the protocol and any amendments

• monitor compliance with previous SSC recommendations

2.4 Agreement and conflicts of interest

The independent SSC members will not be asked to formally sign a contract but should formally register their agreement to join the group by confirming (1) that they agree to be a member of the SSC and (2) that they agree with the contents of this Charter. Competing interests should be disclosed at this time. These are not restricted to financial matters – involvement in other studies or intellectual investment could be relevant. Although members may well be able to act objectively despite such connections, complete disclosure enhances credibility (see Annexe 1). SSC members should not use any study data to inform trading in pharmaceutical shares, and careful consideration should be given to trading in stock of companies with competing products. Changes in declarations of real or potential competing interests should be declared at the start of each meeting.

3. Before or early in the trial

3.1 SSC input into the protocol

All potential independent SSC members should have opportunity to comment on the protocol as early as possible. I-TRAC has been reviewed by the Sponsor, Funder and the research ethics committee. Therefore, if a potential independent SSC member has major reservations about the study (eg the protocol, the logistics, ethical concerns) they should report these to the Chief Investigator and may decide not to accept the invitation to join. SSC members should be constructively critical of the ongoing study, but also supportive of aims and methods of the study.

3.2 Timing of first SSC meeting

The first meeting of the SSC will take place early in the course of the study, to discuss the protocol, the study, future meetings and to enable the SSC independent members to clarify any aspects with the principal investigators.

4. Composition

4.1 SSC membership

The SSC has a minimum of 75% majority of independent members. The independent members of the I-TRAC TSC are: [name] (Chair) [name] [name] [name]

The University of Aberdeen insurance policies cover the activities of the SSC independent members for their work on the committee.

The Chief Investigator ([name]) or an appropriate deputy, is also a member. The other I-TRAC grantholders and key members of the central office (e.g. the trial manager) may attend SSC meetings but are not members. The funder and Sponsor will be notified in advance of meetings and a representative invited to attend. Other relevant experts may be invited to attend as appropriate. Quoracy and voting rights are described in sections 7.3 and 7.4.

4.2 Responsibilities of the Study Office

The Chief Investigator and staff from the Study office will produce a short report on the study before each meeting of the SSC, including an update on recruitment, retention and serious adverse events.

4.3 Responsibilities of the Facilitator

The Facilitator will be responsible for arranging meetings of the SSC, coordinating reports, producing and circulating minutes and action points. The Facilitator will be the central point for all SSC communications between the SSC and other bodies, will be copied into all correspondence between SSC members and will be kept aware of trial issues as they arise.

4.4 Relationship between study committees

The responsibilities of each trial committee are detailed in the protocol and in the respective Charters.

5. Organisation of meetings

5.1 Frequency

The SSC will meet approximately annually. At the request of the SSC, interim meetings, in person or by teleconference, will be organised. Major study issues may need to be dealt with between meetings, by phone or by email. SSC members should be prepared for such instances.

5.2 Attendance

Effort will be made to ensure that all members can attend. The CI or a deputy will try to attend all meetings, especially if major actions are expected. Members who cannot attend in person should be encouraged to participate by teleconference.

The meeting report will be circulated at least one week before the meeting in order to enable SSC members who will not be able to attend the meeting to pass comments for consideration during the discussions at the meeting to the Facilitator, SSC Chair and/or CI.

5.3 SSC payments

I-TRAC SSC members will be reimbursed for travel and accommodation. No other payments or rewards are anticipated. However, a fee is paid to members of the public which covers their contribution to the trial, e.g. for meeting attendance and preparation work. The fee will be paid by the University of Aberdeen as it is part of the grant award from the NIHR. Members of the public are responsible for paying appropriate income tax and National Insurance contributions and must make their own arrangements for this.

5.4 Independent members who fail to attend meetings

If an independent member does not attend a meeting or provide comments when requested between meetings, it should be ensured that the independent member is available for the next meeting. If an independent member does not attend the next meeting or provide comments when next requested, they should be asked if they wish to remain part of the SSC. If an independent member does not attend a third meeting, strong consideration should be given to replacing this member.

5.5 Resignation and replacement of independent members due to change in circumstances

If an independent Committee member's circumstances change (eg if he/she moves job to the same institution as the CI) he/she would resign from the committee. A replacement independent member would be identified and appointed.

6. Study documentation and procedures to ensure confidentiality and proper communication

6.1 Material to be considered during meetings

A short report will be prepared by the central co-ordinating office. This will report on accrual and any matters affecting the study (e.g. results of pilot/feasibility study). Additionally, the material may include requests from the PMG or draft publications. Where relevant, accrual, compliance with and collection of primary and key secondary outcomes, treatment may be presented by centre.

6.2 Accumulating data

The accumulating study data will be reviewed by the SSC.

6.3 External evidence

It is the responsibility of the PMG to make the SSC aware of any external evidence (e.g. from other studies, trials/systematic reviews) and possible impact on I-TRAC at SSC meetings.

6.4 Retention of papers after the meeting

The central co-ordinating office will keep a central record of all minutes, reports and correspondence by the SSC. SSC members will be expected to delete, destroy or store securely copies of the reports to and from the SSC, agenda and minutes, as well of copies of communications between meetings. All documentation should be considered confidential.

7. Decision making

7.1 Possible SSC decisions/recommendations

Possible decisions could include:

- No action needed, study continues as planned
- Modifying target recruitment, or pre-analysis follow-up, based on any change to the assumptions underlying the original study design.
- Sanctioning and/or proposing protocol changes

7.2 SSC decision making methods

Every effort should be made to achieve consensus. The role of the Chair is to summarise discussions and encourage consensus; therefore, it may be best for the Chair to give their own opinion last. It is important that the implications (e.g. ethical, statistical, practical and financial) for the study be considered before any decision is made.

7.3 When the SSC is quorate

The minimum quoracy for a meeting to conduct business is 67% of appointed members. Therefore at least members of the SSC should be expected to be present including the Chair.

If, at very short notice, a SSC member who was expected to participate cannot do so, the SSC meeting may still go ahead at the discretion of those present. In such cases, if the SSC has considered a major action or recommendation, the SSC Chair (or, in the absence of the Chair, the independent member who has chaired the meeting) should communicate with the absent members as soon after the meeting as possible to check they agree. If they do not agree, a further meeting/teleconference should be arranged with the full SSC.

